2. STUDY PROCEDURES

a. Procedures

Screening

Subjects will undergo medical, psychological and neuropsychological assessments to assure compliance with all inclusion and exclusion criteria. Eligible subjects will receive active iTBS.

TMS Treatment

All treatments and motor threshold determinations will be completed by physicians or other health care providers who have been trained to the process based on the MagVenture User Manual and certified by the department. All processes are consistent with the clinical use of the MagVenture MagPro rTMS research system.

iTBS sessions will occur approximately 2 days after the baseline session with week daily sessions delivered to left DLPFC over 6 weeks. We will start with the currently FDA approved iTBS protocol for adults. Stimulation will be administered using the MagVenture MagPro rTMS Research System at currently FDA approved parameters: 80% of the active motor threshold, 20 cycles of 10 bursts of 3 pulses at 50Hz delivered in 2 second trains with an 8 second inter-train interval. The stimulation will be applied for

3 min delivering a total of 1800 pulses/session. These stimulation sessions will occur daily (week days) for 6 weeks. Resulting in a total of 30 sessions. Motor Threshold (MT) Determination: MT Location and MT Level - The motor threshold location will be determined by visual confirmation of the location on the motor cortex that controls the abductor pollicis brevis (APB) muscle of the thumb. The resting MT level is the minimum power to produce a stimulation response 50% of the time.

Prophylactic use of acetaminophen or ibuprofen will be allowed for subjects reporting sensations at or near the stimulation site which are uncomfortable or painful. During the first week of treatment only, in the event that the subject cannot tolerate the treatment at these dose parameters, dose intensity may be titrated downward to 110% of the motor threshold, with all other dose parameters remaining the same.

Heart Rate Variability (HRV)

Participants will have their HRV measured before they receive any stimulation, at the end of each stimulation week and at the end of the six week treatment course. HRV will be measured using ECG electrodes attached to the wrists and an r-wave trigger device (neuroConn, Ilmenau, Germany). HRV will be measured when viewing videos depicting negative emotions (e.g. anger, fear) and when viewing neutral stimuli.

Structural/Functional Brain MRI

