4. RADIOISOTOPES OR RADIATION MACHINES

N/A

5. DEVICES USED IN THE STUDY**a. Investigational Devices (Including Commercial Devices Used Off-Label)**

Investigational Device 1	
Name:	TMS Magnet (MagVenture)
Description:	Transcranial Magnetic Stimulation
Significant Risk? (Y/N)	No
Rationale for Non-Significant Risk	Device within FDA specified parameters (iTBS).

b. IDE-Exempt Devices

N/A

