9. RISKS

a. Potential Risks

i. Investigational devices

Anticipated Risks

Seizures

Repetitive transcranial magnetic stimulation is generally regarded as safe and without any serious or lasting adverse effects (Wasserman 1998; Rossi 2009). Inadvertent induction of a seizure is the most medically significant potential safety concern. However, there is no known risk of seizure for the above-stated brain stimulation parameters. The motor threshold is reflective of stimulation output necessary to cause neuronal depolarization. Since its first use in 2005, only one case of TBS has resulted in seizure, which occurred for stimulation at >100% resting MT (120% of aMT) and this was continuous TBS not iTBS. This proposed protocol involves iTBS delivered at 80% motor threshold. Finally, the proposed stimulation parameters mirror those used in Stanford IRB-approved iTBS protocols (Protocol Director [name]; ID 33797, ID 38138), which have received a “minimal risk” designation.

Studies evaluating the safety of iTBS in adolescents have shown it to be minimal risk (Hong et al., 2015; Wu et al., 2012).

Safety Monitoring for Potential Seizure Risk

Safety monitoring for the potential risk of seizure is addressed in several ways in this protocol. All subjects will be assessed during the screening phase for neurologic disease, concurrent medication use, or other clinical factors that may contribute to the risk of seizure. The Transcranial Magnetic Stimulation Adult Safety Screen (TASS) will be used as a screening tool to assure rigorous review of these clinical factors. Stimulation parameters have been selected to optimize the likelihood of clinical efficacy, while maintaining a safety level within the guidelines consistent with the 1998 NINDS workshop recommendations (Wasserman 1998).

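### The week-1 intolerance rule lowers the dose to 110% of an unnamed motor threshold from a start of 80% of active threshold, and only the resting threshold is defined

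*Combined protocol and SAP*

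**What the plan says.** The starting intensity, in the TMS Treatment part of protocol section 2.a, is "80% of the active motor threshold", presented as the FDA-approved adult iTBS setting.

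The same part has a tolerability rule that applies in the first week only, to a subject who cannot tolerate those settings: "dose intensity may be titrated downward to 110% of the motor threshold, with all other dose parameters remaining the same". It does not say whether this is the active or the resting threshold.

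The threshold determination text, also in 2.a, locates the thumb area of the motor cortex by visual confirmation and then defines one level: "The resting MT level is the minimum power to produce a stimulation response 50% of the time". It gives no definition or procedure for the active threshold. Operators are to be "trained to the process based on the MagVenture User Manual".

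Section 9.a.i (Seizures) states that "there is no known risk of seizure for the above-stated brain stimulation parameters". It describes one seizure with theta-burst stimulation, "which occurred for stimulation at >100% resting MT (120% of aMT) and this was continuous TBS not iTBS", and then gives this trial's intensity: "This proposed protocol involves iTBS delivered at 80% motor threshold". Again the type of threshold is not named.

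Section 5.a bases the non-significant-risk classification on the device staying within the iTBS parameters that the FDA has specified.

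Section 9.c returns to discomfort during treatment. It offers coil repositioning and analgesics and gives no intensity step.

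**The concern.** A rule meant to make treatment more tolerable carries a number that makes it stronger. It applies to participants aged 12 to 21 who have already been unable to tolerate the starting dose. An operator who follows the figure raises the intensity. One who follows the direction has no figure to use.

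Two further points follow from the same text:

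- **Safety case.** The seizure statement and the non-significant-risk rationale are both tied to the starting parameters. As written, neither extends to a 110% step.
- **Dose reference.** The dose is a percentage of one threshold and the protocol defines another. This concerns the ordinary dose of all 30 planned subjects, not only those who need a lower one.

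**Working it through.** **Inputs**

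| Quantity | Value | Source |
|---|---|---|
| Starting intensity | 80% of active threshold (aMT) | 2.a, TMS Treatment |
| Intensity after a downward step | 110% of a threshold of unstated type | 2.a, TMS Treatment |
| Threshold level defined | resting (rMT) only | 2.a, MT determination |
| Intensity in the seizure argument | 80% of a threshold of unstated type | 9.a.i |
| r = rMT/aMT in participants | not given; assumption | none |

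**Step 1: both percentages on one threshold.** The ratio of new to starting intensity is 110/80 = 1.375, an increase of 37.5%. The result is the same whether both are active or both are resting, and it needs no assumption about r. For 110% to be a reduction on one scale, the start would have to be above 110%. No section gives such a start.

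**Step 2: start on active, step on resting.** The new intensity as a percentage of aMT is 110 × r, and the ratio to the start is 110r/80 = 1.375r. It is a reduction only if 1.375r < 1, that is, r < 80/110 = 0.727.

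| Assumed r | Step as % of aMT | Ratio to start |
|---|---|---|
| 0.70 | 77.0 | 0.96 |
| 0.727 | 80.0 | 1.00 |
| 0.80 | 88.0 | 1.10 |
| 1.00 | 110.0 | 1.375 |
| 1.20 | 132.0 | 1.65 |
| 1.50 | 165.0 | 2.06 |

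The only information on r in the documents is the seizure case in 9.a.i. There 120% of aMT exceeded 100% of rMT, so r was below 1.2 in that one person. This says nothing about r in participants, and the upper rows only show the range. The direction of the error is the same for every r above 0.727.

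**Step 3: set against the safety case.** Section 9.a.i argues from 80%; the step is 110%. If 110% means resting threshold, it exceeds 100% of resting by definition, and exceeding 100% of resting is one of the features that 9.a.i uses to set the seizure case apart. The other is that the case was continuous TBS, which this trial does not use. So no seizure risk is inferred here, only that the argument does not reach 110%.

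**Step 4: the ordinary dose.** An operator who applied 80% to the only threshold level defined in the protocol would deliver 80 × r percent of aMT. At r = 1.0 that is the intended 80%. At an assumed r = 1.2 it is 96% of aMT, and 96/80 = 1.2 times the intended dose.

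**Step 5: look for a correction elsewhere.** Section 9.c has the repositioning and analgesic measures without an intensity, followed by a stranded fragment limiting something to the first week. That suggests, without proving it, that the titration clause was removed there and left in 2.a. It supplies no replacement figure.

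**The case against.** The strongest reply is that the clause is unlikely to cause over-stimulation. It is permissive, and its stated direction is down. A trained operator who reads both the direction and the number finds no step that satisfies both and would probably leave the intensity alone or reduce it by judgement. Section 9.c also allows iTBS to be stopped, and section 9.d lets the investigator withdraw a subject for safety reasons, so an intolerant subject has safe options without this clause. On that view it is an editing slip that leaves a rule unusable, and the point about the safety case matters only if 110% is actually delivered.

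Much of this stands. Exposure to 110% is not established, and the safety-case point is secondary. It does not repair the rule, however: 110% is the only alternative intensity the protocol names, and an operator who disregards it must improvise or stop.

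On the threshold definition, staff are trained from the device manual, which may describe the active threshold. That manual is not among the documents, so it cannot be said that operators lack a method, only that the protocol does not state one. The documents also leave open which label is the slip, active in the dose or resting in the determination text.

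Finally, no sample size, endpoint or analysis depends on this. It is an internal inconsistency in a dosing rule. That is correct, and the case for changing it rests on participant safety.

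**Conclusion.** The concern holds. As written, the week-1 rule labels an increase as a decrease. The size is 37.5% if both percentages refer to the same threshold, which needs no assumption. If 110% means resting threshold, the size is 1.375 × r times the start, at least a 37.5% increase on the assumption that resting is not below active. Only a resting threshold under 72.7% of active would make the rule a true reduction.

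The limits of the protocol's safety argument and the missing active-threshold definition are confirmed as secondary points. The likely harm is bounded by operator judgement and the option to stop. The rule should still be corrected, because a tolerability safeguard for a largely adolescent population has no usable step.

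**What to change.** 1. In section 2.a, delete the 110% figure and state a true reduction. Suggested wording: *In week 1 only, a subject unable to tolerate 80% of the active motor threshold may have the intensity reduced to X% of the active motor threshold, where X is below 80; the remaining stimulation settings do not change.* The sponsor must supply X, since the documents do not show what was intended.
2. Make the threshold determination text describe the threshold on which the dose is based. If active threshold stays, add how it is measured. If resting was intended, restate the starting dose and X on that scale.
3. Name the same threshold type in section 9.a.i.
4. If an intensity above 80% really is intended, extend the seizure statement in 9.a.i and the non-significant-risk rationale in 5.a to cover it.

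The cost is a wording amendment with IRB review, plus a short description of the active-threshold measurement if that remains the basis. No visit or data item is added.

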3. BACKGROUND

a. Past Experimental and/or Clinical Findings

rTMS Therapy System Mechanism of Action

The MagVenture TMS Therapy® System is a computerized electromechanical instrument that produces and delivers brief duration, rapidly alternating (pulsed) magnetic fields to induce electrical currents in localized regions of the cerebral cortex. Since TMS therapy produces a time varying magnetic field, its intended effect derives fundamentally from Faraday’s Law, which asserts that a time-varying magnetic field produces an electrical current in an adjacent conductive substance. During TMS, the conductive substance of interest is the brain, in particular the region of the cortex that lies beneath the treatment coil.

The electric current induced in this region of the cortex travels in a path orthogonal to the direction of the alternating magnetic field with the point of maximum field strength and greatest current located directly beneath the center of the coil, which is the TMS system component that rests against the patient’s head and transmits magnetic pulses to the patient’s brain. The induced current is tangential to the scalp at the cortical surface, and diminishes in magnitude with increasing depth.

In the targeted area of the motor cortex, where field strength achieves the stimulation threshold, it is postulated that neuronal depolarization occurs. The peak magnetic field strength achieved with each pulse in the cortex is approximately 0.5 Tesla.

Although the mechanism of action is unknown, it is hypothesized that TMS causes direct neuronal depolarization in brain regions immediately adjacent to the magnetic coil, and

also results in changes in functional activity in areas of the brain that are synaptically connected to the brain regions experiencing direct neuronal depolarization. It is thought that these actions may cause various physiologic changes in the brain which are associated with the symptomatic relief of depression in patients.

Efficacy and Safety of TMS in Major Depression in Adult Patients

The efficacy and safety of TMS in adult patients with major depressive disorder (MDD) who failed to receive satisfactory improvement from prior antidepressant medication was established in two randomized controlled trials (O'Reardon2007; Janicak 2008; George 2010; Li et al., 2012). Clinical efficacy outcomes of the use of TMS in adult patients with major depression in real world clinical practice was demonstrated in a multisite naturalistic study in 42 US centers under conditions of general clinical use (Carpenter, 2012; Janicak2013).

A randomized controlled trial funded by the National Institute of Mental Health, evaluated the safety and efficacy of TMS using a clinical trial version of the NeuroStar TMS Therapy System in adult patients (N=197, 4 sites) with moderate to severe major depressive disorder and who failed to benefit from 1 through 4 adequate antidepressant medication trials, as defined using the Antidepressant Treatment History Form (ATHF), or who could not tolerate 3 or more antidepressant medications (George 2010). The study evaluated 197 outpatients across 4 sites, ages 21-70 years, most with a recurrent course of major depression (~97%), with the maximum duration of the current episode of depression of ≤ 3 years. Patients had received a median of 1.6 total prior antidepressant medications at an adequate dose and duration in the current episode or a median of 4 treatment attempts at any dose and duration. The primary outcome measure was remission using the HAMD24 (HAMD24 total score ≤ 3 or 2 consecutive HAMD24 total scores <10) through 6 weeks of acute treatment. A statistically significant benefit of active TMS as compared to sham treatment for the HAMD24 remission outcome (Active TMS: 13.4% vs Sham TMS: 5.0%, P=0. 0173) was observed in the ITT study population (N=197). An adjusted odds ratio of achieving remission with active TMS was 4.05 (95% confidence interval (CI), 1.28- 12.83) as compared to sham TMS. The baseline to endpoint change score outcome using the HAMD24 also favored active TMS compared to sham treatment (-2.11, 95% CI: -4.30, 0.08; P=0.0588). Baseline to endpoint outcomes for patients treated with active TMS were statistically significant as compared to sham treatment as measured using the MADRS (P=0.0136), CGI-S (P=0.0181) and the patient-rated IDS-SR (P=0.0008). For the categorical endpoints, higher rates of remission were observed for patients receiving active TMS as compared to sham treatment as measured using the MADRS (P=0.0170) and the patient-rated IDS-SR (P=0.1199), and for response (50% improvement from baseline) for all three measures (HAMD24, P=0.0104; MADRS, P=0.0063; IDS-SR, P=0.0145). Standardized effect size estimates for the continuous outcome endpoints range from 0.43 to 0.67, indicating a moderate to large effect size in this patient population.

Efficacy of TMS for the treatment of adolescent depression, for all TMS devices including the NeuroStar TMS Therapy® System, has been reported in two pilot clinical studies and in multiple case reports (Walter 2001; Bloch 2008; Wall 2011). These open-

label studies describe the treatment of 24 patients, ages 10-18. The 2011 Wall et al. open-label trial is the only study that used the NeuroStar TMS Therapy System. This study reported on the treatment of 7 antidepressant-resistant adolescents and demonstrated a robust response rate noted by 5 of 7 subjects achieving remission of depression, as rated using the Childhood Depression Rating Scale – Revised (CDRS-R). Furthermore, CDRS-R mean depression severity scores were significant by treatment 20 as compared to baseline with similar efficacy demonstrated using the patient reported Quick Inventory of Depressive Symptoms – Adolescent Version (QIDS-A17- SR). Placebo effects in open-label trials of adolescents are a well-known phenomenon. However, adolescents demonstrate enduring mood improvement for at least 6 months following their final acute treatment (session 30). Furthermore, 7 of 8 subjects completed the entire treatment course, with 1 patient exiting the study after only 5 minutes of treatment due to scalp discomfort and a perceived lack of improvement.

iTBS has been shown to be more effective at inducing antidepressant responses in adults than traditional rTMS. 3 minutes of iTBS induce equivalent antidepressant responses as 37 minutes of traditional rTMS stimulation (Blumberger et al., 2015) and lower stimulation intensities are required to induce antidepressant responses (Wu, Shahana, Huddleston, Lewis, & Gilbert, 2012).

The shorter stimulation times and the lower stimulation intensities required for iTBS in comparison to traditional rTMS make iTBS potentially advantageous method for adolescents with MDD. Traditional rTMS has been shown to be effective at reducing depressive symptoms in adolescents (Carpenter et al., 2012) but iTBS has not been trialled in adolescents with MDD. Initial trials investigating the safety of iTBS in adolescents have identified iTBS as minimal risk (Hong et al., 2015; Wu et al., 2012).

It is clear that the dorsolateral prefrontal cortex is heavily implicated in the pathophysiology of depression. The left DLPFC is hypoactive in depressed patients and is associated with negative emotional judgment (Grimm et al., 2008). Additionally, the DLPFC is a component of the cognitive control network (CCN) and the modulation of this node appears to modulate the CCN. At least four groups have performed iTBS to the DLPFC in adults and have seen antidepressant effects (Chung et al., 2015; Desmyter et al., 2016; Duprat et al., 2016).

Safety of TMS in adolescent depression:

rTMS and iTBS have been well tolerated in pediatric populations, with reports of mild adverse events that bear only minimal risk to children. Risk from stimulation protocols (e.g. high frequency TMS and theta-burst) in children has been deemed to be similar to that in adults.

b. Findings from Past Animal Experiments

N/A

4. RADIOISOTOPES OR RADIATION MACHINES

N/A

5. DEVICES USED IN THE STUDY**a. Investigational Devices (Including Commercial Devices Used Off-Label)**

Investigational Device 1	
Name:	TMS Magnet (MagVenture)
Description:	Transcranial Magnetic Stimulation
Significant Risk? (Y/N)	No
Rationale for Non-Significant Risk	Device within FDA specified parameters (iTBS).

b. IDE-Exempt Devices

N/A

6. DRUGS, BIOLOGICS, REAGENTS, OR CHEMICALS USED IN THE STUDY

N/A

7. DISINFECTION PROCEDURES FOR MEDICAL EQUIPMENT USED ON BOTH HUMANS AND ANIMALS

N/A

8. PARTICIPANT POPULATION**a. Planned Enrollment**

A total of 30 subjects are expected to enroll at Stanford. All subjects will have single or recurrent depression of moderate or greater symptom severity.

b. Age, Gender, and Ethnic Background

Male and Female Outpatients between the ages of 12-21 yo of any ethnic background will be recruited.

c. Vulnerable Populations

All of the subjects enrolled into this trial are adolescents per the FDA definition. The TMS treatment is being investigated for efficacy and safety in the adolescent population that experiences major depression. TMS is currently FDA approved for the treatment of MDD in adults.

d. Rationale for Exclusion of Certain Populations

Women, minorities, non-English speaking individuals, or children are included in enrollment.

e. Stanford Populations

Stanford laboratory personnel, employees, and/or students will not be specifically sought, they will also not be excluded from participation.

f. Healthy Volunteers

No healthy volunteers.

g. Recruitment Details

We anticipate a majority of the recruitment will also come from the outpatient child psychiatry clinic.

Several resources will be utilized for recruitment of potential subjects including: from within the clinical and referral practices of the clinical study site

- referrals from other care providers within the treatment communities
- radio advertisements
- invitation letters sent to parents of potentially eligible subjects
- print advertisements, including but not limited to brochures, flyers, Craig's List, and listings in research classifieds
- trial listing with ClinicalTrials.gov
- trial listing on university and clinical study site website
- social media

We will also begin utilizing the Stanford Research Registry (protocol 25422) to recruit 30 study participants. The research registry is a list of individuals who have consented to be contacted by researchers at Stanford and at present includes over 1,000 volunteers.

h. Eligibility Criteria

i. Inclusion Criteria

- 1) Ages 12-21 years of age;
- 2) with at least moderate to severe depressive symptoms confirmed by the Children's Depression Rating Scale-Revised (CDRS-R>40);
- 3) able to commit to protocol schedule and provide Informed consent by a legal guardian and assent by a youth participant;
- 4) have had at least one prior antidepressant treatment failure with adequate dose and duration.
- 5) Display low heart rate variability (HRV) at baseline

ii. Exclusion Criteria

- 1) No prior neurological diagnosis (neurodevelopmental disorders, strokes/traumatic brain injuries, brain tumor, epilepsy);
 - Antecedent seizures
 - Any condition likely to be associated with increased intracranial pressure
 - Space occupying brain lesion
 - of cerebrovascular accident

- Transient ischemic attack within 2 years
- Cerebral aneurysm
- Dementia
- Brain surgery
- Head trauma with loss of consciousness for >5 minutes
- History of stroke
- History and/or family history of epilepsy

- 2) No contraindications for TMS or MRI e.g. have any implanted metal;
- 3) Unstable medical conditions
 - Hematological or infectious (e.g., human immunodeficiency virus-HIV) disorders.
 - History of autoimmune, endocrine, viral, or vascular disorder
 - Unstable cardiac disease, uncontrolled hypertension, or sleep apnea
 - Current anticoagulant, immune suppressive, and/or chemotherapy or those who have received any of these therapies within 3 months before enrollment in the study.
- 4) Acute suicide risk as defined by the investigator
- 5) Pregnancy, suspected pregnancy or not on birth control if sexually active;
- 6) Inability to locate and quantify a motor threshold; and
- 7) Any factor that the PI determines to be reason for exclusion.

i. Screening Procedures

Following the informed consent process, enrolled subjects will begin the study eligibility screening process. Verification of inclusion and exclusion will be completed by the study physician to ensure that the subject is eligible for the study and that it is safe for them to participate.

j. Participation in Multiple Protocols

The consent form clearly asks patients if they are participating in any other research studies. The PI and/or research coordinator will also ask the patient. If patients are currently participating in another protocol, the PI will determine if it is appropriate to continue the participation.

k. Payments to Participants

Participants will be paid \$50.00 per MRI scan.

l. Costs to Participants

All procedures are covered by the study. There may be additional costs incurred for the personal time it will take for participants to come to study appointments.

m. Planned Duration of the Study

The estimated duration of the entire study is two years. Screening a participant may take 4-6 hours, and active participation would involve daily iTBS treatments for 6 weeks. Analyses of participant data may take up to 2-3 years.

